6.1. Analysis of Primary Efficacy Endpoint

The primary efficacy endpoint is the proportion of adult patients in clinical remission (Three-component Mayo definition) at Week 10. The null and alternative hypotheses for the primary efficacy endpoint are:

Null hypothesis H_0 : Clinical remission_{RPC1063} = Clinical remission_{Placebo}

Alternative hypothesis H_a : Clinical remission_{RPC1063} \neq Clinical remission_{Placebo}

6.1.1. Primary Analysis

The primary analysis of the primary endpoint of proportion of patients in clinical remission (Three-component Mayo definition using 7-day scoring algorithm, see [Appendix 3.2](#)) at Week 10 will be carried out in the ITT population using Cochran-Mantel-Haenszel (CMH) test at two-sided 5% level of significance, stratified by corticosteroid use at screening (yes or no), and prior anti-TNF use (yes or no). Results will be expressed as number of patients in remission, remission percentages, weighted difference in remission percentages, odds ratio, and associated two-sided 95% confidence intervals (CIs) and p-values. A bar graph showing the percentages of patients in clinical remission by treatment/cohort with the weighted treatment difference and CMH p-value will be produced. See [Appendix 6](#) for some sample SAS codes.

For patients whose clinical remission (Three-component Mayo definition) at Week 10 cannot be adequately determined (including missing data, discontinuation or lost to follow-up), their clinical remission will be imputed using a non-responder imputation (NRI) approach as described in [Appendix 1.3](#). Patients meeting the TFR criteria prior to the Week 10 visit, their clinical remission at Week 10 will be imputed using NRI as described in [Appendix 1.3](#).

6.1.2. Sensitivity Analyses

Sensitivity analyses will be performed to support the primary analysis ([Table 2](#)). These analyses use missing data handling methods including multiple imputation (MI) [REDACTED] all observed data and tipping point analysis [REDACTED]

Tipping Point Analysis

A tipping point (TP) sensitivity analysis for the primary endpoint, clinical remission (Three-component Mayo definition) at Week 10, will be performed. The TP method is considered as an alternative strategy for handling missing data [REDACTED] and the analysis for clinical remission (Three-component Mayo definition) at Week 10 will follow the algorithm for a binary variable provided in the [REDACTED]. This analysis will include all observed data and then vary assumptions about the missing outcomes, by assigning remitters to some missing data and non-remitters to other missing data in the two treatment arms. Tipping point is defined here as the difference in the number of remitters (for clinical remission at Week 10) between the two treatment groups in the missing part at which the study conclusion changes. Unlike the non-responder imputation (NRI) which assigns all missing data to a non-responder for the Week 10 clinical remission, a TP analysis replaces the missing value with either remitter or non-remitter so that the resulting treatment comparison, or level of significance between the two arms, varies. Analysis of each of the imputed dataset will be carried out using the same method for the primary analysis as described in Section 6.1.1. Conducting these sensitivity analyses using the proposed missing data handling methods (NRI, tipping point and multiple imputation), will

support that the comparison of the two treatment groups in clinical remission at Week 10 is robust under different missing data imputation methods.

Multiple Imputation (MI)

A multiple imputation procedure replaces each missing value with a set of plausible values that represent the uncertainty about the right value to impute. These multiply imputed data sets are then analyzed by using standard procedures for complete data and combining the results from these analyses [REDACTED]

The following process will be carried out MI for the primary endpoint, clinical remission (3 component Mayo definition) at Week 10. Because clinical remission and response are determined using a 3- component subscores: Rectal Bleeding (RB), Stool Frequency (SF) and Endoscopy subscore, MI will be applied to each of the 3 component subscores followed by applying the definition to determine clinical remission and/or response at Week 10.

The missing data pattern will be examined first. The missing data for RB, SF and Endoscopy subscores is expected to follow either monotone pattern or arbitrary (non-monotone) for each of the three subscores.

- When a subscore (e.g., RB) is considered to follow a monotone missing pattern for a particular individual at a given time point (e.g. Week 5), it implies that all subsequent visits (Weeks 5 and 10) are missing for that individual. For data sets with monotone missing patterns, the variables with missing values can be imputed sequentially, with data from the 2 visits (Weeks 5 and 10) use a logistic regression method (adjusting for the two stratification factors and other baseline covariates deemed appropriate).
- A full conditional method (FCM) will be applied when a subscore (RB or SF) is considered to follow an arbitrary missing pattern.

Combining inferences from imputed datasets involves the following three steps:

- The missing data are filled in $m=20$ times to generate m complete data sets.
- The $m=20$ complete data sets after MI are analyzed using the primary analysis method outline in Section 6.1.1.
- The results from the $m=20$ complete data sets are combined for the inference.

The above MI process results in valid statistical inferences that properly reflect the uncertainty due to missing values; for example, valid confidence intervals for parameters.

The inference of the tipping point analysis will be made based on several factors including missing data pattern, reasons of subject discontinuation/drop-out, results from all observed (non-missing) data and clinical remission results in the published historical studies.

All these analyses (sensitivity and tipping point) will be performed using SAS.

In addition the primary analysis will also be repeated on each of the subgroups listed in Section 6.4. The subgroup analyses will be reported in a table and a forest plot showing the weighted treatment differences with associated 95% CI and p-values will be produced.

These will be considered sensitivity/supportive analyses only and will not be subject to family-wise Type I error control. The analyses below will be calculated using the three-component Mayo definition with 7-day scoring algorithm (Appendix 3.2), unless specified otherwise.

Table 2: Sensitivity Analyses for the Primary Endpoint

Analysis/Endpoint Description	Imputation	Population
Clinical remission – Observed Cases	None	ITT
Clinical remission – Tipping Point Analysis	TPA	ITT
Clinical remission – Multiple Imputation	MI	ITT
Clinical remission	NRI	PP
Clinical remission – 14-day Scoring Algorithm (A, B)	NRI	ITT
[REDACTED]		
[REDACTED]	■	■
[REDACTED]	■	■
[REDACTED]	■	■
[REDACTED]	■	■

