13. PLANNED STATISTICAL METHODS

13.1. Determination of Sample Size

Induction Period:

Cohort 1 (adult patients): Based on results from a previous Phase 2 induction trial of RPC1063 1 mg, it is anticipated that at least 16% of patients in the RPC1063 group and approximately 6% of patients in the placebo group will be in clinical remission at the end of the IP. Based on a 2-sided Fisher's exact test at $\alpha = 0.05$, a sample size of approximately 600 patients randomized in a 2:1 ratio in Cohort 1 (400 RPC1063 1 mg and 200 placebo) will provide at least 90% power to detect this difference of 10 percentage points.

Cohort 2 (adult patients): Based on the same Phase 2 trial, it is anticipated that at least 60% of patients treated with RPC1063 will have a clinical response at the end of the IP. In order to ensure that there are approximately 420 patients with a clinical response to RPC1063 for potential enrollment of approximately 400 patients into the MP (assuming a 5% dropout rate), it will be necessary to enroll approximately 900 adult patients overall into the IP, of which 700 will receive treatment with RPC1063. Therefore, approximately an additional 300 patients receiving RPC1063 1 mg will be enrolled into Cohort 2.

Table 5: Sample Size and Corresponding Precision

Total Sample Size	Sample Size by Treatment		Precision: Half-Width of a 95% Confidence Interval for Treatment Difference (Ozanimod Versus Placebo)	
	Ozanimod	Placebo	Clinical Remission $\Delta=10\%$ (16% versus 6%)	Clinical Response $\Delta=25\%$ (57% versus 32%)
30	20	10	21.8%	36.1%
60	40	20	15.4%	25.6%
90	60	30	12.6%	20.9%
120	80	40	10.9%	18.1%
150	100	50	9.7%	16.2%

Maintenance Period (adult patients):

The placebo remission rate at Week 42 (52 weeks total treatment) is assumed to be 16% in a randomized withdrawal trial in UC patients who have previously had a clinical response to induction therapy (Feagan et al, 2013). Based on a 2-sided Fisher’s exact test at alpha = 0.05, a sample size of 400 patients (200 patients per treatment group) will provide 90% power to detect a statistically significant improvement in the remission rate of 14 percentage points or larger (ie, an active group remission rate of 30% or higher). To account for a 5% rate of patients who had a clinical response to induction therapy with RPC1063 not entering the MP, approximately 420 patients with a clinical response to RPC1063 will be required at the end of the IP.

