6.2.2. Primary Analysis of Key Secondary Efficacy Endpoints

The clinical response determined using the 7-day scoring algorithm (Appendix 3.2) and the other two key secondary endpoints (endoscopic improvement and mucosal healing) will be tested using the same type of CMH test as specified for the primary endpoint. For each key secondary endpoint, the same summary and inferential statistics will be reported as specified for the primary analysis of the primary endpoint in Section 6.1.1, including a bar graph showing the percentages by treatment/cohort with the weighted treatment difference, associated two-sided 95% CI and CMH p-value.

Patients without sufficient data to determine clinical response at Week 10 will be analyzed using NRI as described in Appendix 1.3. Patients without central read endoscopy results to determine endoscopic improvement at Week 10 will be analyzed using NRI. Patients without endoscopy or Geboes index results to determine mucosal healing at Week 10 will be analyzed using NRI.

For all key secondary endpoints, patients meeting the TFR prior to the Week 10 efficacy evaluation will be analyzed using NRI as described in Appendix 1.3.

The analysis of each key secondary endpoint will be repeated on each of the subgroups listed in Section 6.4. In addition to reporting the subgroup analyses out in a table, a forest plot showing the weighted treatment differences with associated 95% CI and p-values will be produced.

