6.4. Subgroup Analysis

Subgroup analyses will be performed for the endpoints of clinical remission and clinical response only using the three-component Mayo score based on a 7-day scoring algorithm ([Appendix 3.2](#)). For each specific subgroup, if there are not enough patients (i.e., <5% ITT population), the corresponding analyses will not be performed. The following are the pre-defined subgroups:

1. Corticosteroid use at screening (yes vs. no)
2. Prior anti-TNF use (yes vs. no)
3. Baseline complete Mayo score (≤ 9 vs. > 9)
4. Extent of colitis (left-sided vs. extensive)
5. Sex (female vs. male)
6. Age at screening (\leq median vs. $>$ median)
7. Baseline fecal calprotectin (≤ 250 vs. > 250 mg/kg)
8. Baseline ALC ($\leq 1,500$ vs. $> 1,500$ $10^6/L$)
9. Years since initial UC diagnosis (≤ 4 vs. > 4 years)
10. Region (North America, Eastern Europe, Western Europe, Asia Pacific)
11. Baseline partial Mayo score (\leq median vs. $>$ median)

12. Baseline partial Mayo score (≤ 7 vs. >7)

13. Baseline endoscopy subscore (2 vs. 3)

Other subgroups such as race (white vs. non-white), weight (\leq median vs. $>$ median), 5-aminosalicylic acid (5-ASA) use at screening (yes vs. no), and corticosteroid and 5-ASA use at screening (yes vs. no), and moderate UC at screening may also be explored.

[REDACTED]

[REDACTED]

[REDACTED]

[REDACTED]

- [REDACTED]

- [REDACTED]

- [REDACTED]

[REDACTED]

[REDACTED]

[REDACTED]

[REDACTED]

[REDACTED]

[REDACTED]

[REDACTED]

[REDACTED]

- [REDACTED]

- [REDACTED]

[REDACTED]

[REDACTED]

[REDACTED]

- [REDACTED]
- [REDACTED]
- [REDACTED]

[REDACTED]

[REDACTED]

- [REDACTED]
- [REDACTED]

[REDACTED]

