8.1. Demographics

Demographic characteristics including age, age category (18-29, 30-39, 40-49, 50-59, 60-69, 70-75, < 65, ≥ 65, ≤ Cohort 1 median, and > Cohort 1 median), sex, race, ethnicity, weight, height, body mass index (BMI), region (North America, Eastern Europe, Western Europe, Asia Pacific, South America, South Africa), country, and tobacco/nicotine usage (never, former, current) will be summarized for the ITT population and the PP population. Demographic characteristics will also be summarized for All Screen Failures, except weight, height, and BMI, which are not collected for screen failure patients. See reporting convention in [Appendix 1.1](#).

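### Subgroup analyses meant to assess consistency print within-subgroup p-values and, in the visible SAP text, no heterogeneity test; their endpoint and region lists also need aligning

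*SAP*

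**What the plan says.** **Method.** The primary analysis of remission is made "using Cochran-Mantel-Haenszel (CMH) test at two-sided 5% level of significance" (SAP 6.1.1). SAP 6.1.2 repeats it in each subgroup of 6.4, reports the results in a table, and adds that "a forest plot showing the weighted treatment differences with associated 95% CI and p-values will be produced". The same section labels these analyses supportive and outside family-wise error control; Protocol 13.4.1.1 agrees.

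**Purpose.** The V3.0 entry in the SAP's amendment history says that the added subgroups serve to judge whether efficacy is consistent across subgroups. It gives no rule for judging it.

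**Subgroups.** SAP 6.4 lists 13 factors: 12 with two levels, and region with four. On small subgroups it says that "if there are not enough patients (i.e., <5% ITT population), the corresponding analyses will not be performed". Text after the list is blacked out.

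**Endpoints.** SAP 6.4: "Subgroup analyses will be performed for the endpoints of clinical remission and clinical response only". SAP 6.2.2: "The analysis of each key secondary endpoint will be repeated on each of the subgroups listed in Section 6.4". There are three key secondary endpoints: response, endoscopic improvement and mucosal healing.

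**Region.** The subgroup factor in 6.4 is "Region (North America, Eastern Europe, Western Europe, Asia Pacific". The demographic summary in 8.1 uses "region (North America, Eastern Europe, Western Europe, Asia Pacific, South America, South Africa".

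**The concern.** Consistency is a question about the difference between subgroup effects. The only test in the visible text asks something else: whether the effect inside one subgroup differs from zero. That result depends heavily on how many patients the subgroup holds. A reader of the forest plot who sees a non-significant row, for example patients with prior anti-TNF use, may conclude that the drug does not work there when the full planned effect is present.

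Two smaller defects concern which rows appear. A programmer cannot follow both 6.2.2 and 6.4 on endpoints. And patients from South America and South Africa, where SAP 4.1 places sites, fall in no region row, however many there are.

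**Working it through.** **Inputs from the documents.** Protocol 13.1: "it is anticipated that at least 16% of patients in the RPC1063 group and approximately 6% of patients in the placebo group" in remission, 400 versus 200 patients, stated power at least 90% by a two-sided Fisher test at 0.05. Protocol 13.1, precision table: response 57% versus 32%. SAP 4.1: prior anti-TNF use limited to about 30% of Cohort 1.

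**Assumptions.** The documents give no other subgroup shares. I assume prior anti-TNF use in 30%, corticosteroid use in 30% (50% as an alternative), and 50/50 for the other ten two-level factors. The treatment effect is the same in every subgroup.

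**Step 1: the plan's own figure.** Power = Φ[(Δ − 1.96·SE0)/SE1], where SE0 uses the pooled rate, (2 × 16% + 6%)/3 = 12.7%, and SE1 the separate rates. For 400 versus 200: (0.10 − 1.96 × 0.0288)/0.0249 = 1.75, power 96%. Exact Fisher power is also 96.0%, so the stated 90% is met.

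**Step 2: the same formula inside a subgroup, same effect.**

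| Share of Cohort 1 | Patients | SE0 | SE1 | Power |
|---|---|---|---|---|
| 70% | 280 vs 140 | 0.0344 | 0.0297 | 86% |
| 50% | 200 vs 100 | 0.0407 | 0.0352 | 72% |
| 30% | 120 vs 60 | 0.0526 | 0.0454 | 47% |

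Only the size changes down the table. The exact Fisher figures are close (86%, 71%, 43%).

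**Step 3: several rows together.** I simulated trials of 600 patients, 2:1 within the four strata, kept those with an overall CMH p < 0.05, and repeated the CMH test in each row.

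- Prior anti-TNF row, remission 16% vs 6%: non-significant in 48–49% of successful trials.
- At least one of the 24 rows of the 12 two-level factors: 82% (all factors 50/50), 85% (corticosteroid 50/50), 87–88% (base splits); 85–87% if factors are correlated. About 6.1 of 24 rows are non-significant on average.
- With region added (28 rows): about 98–99%.
- Remission at an assumed 20% vs 6%, 12 factors: about 57%.
- Response at 57% vs 32%: about 28% over the 12 factors; 58–88% with region, depending on the regional split.

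**Step 4: what a heterogeneity test would do.** For a two-level factor, z = (d1 − d0)/√(v1 + v0), with d the risk difference in each level and v its variance. Under a uniform effect about 5% of factors are flagged. For 12 independent factors 1 − 0.95^12 = 46%; simulation gives about 47% of successful trials, or 34–42% if the factors are correlated. The test is also insensitive. For prior anti-TNF use, √(0.0454² + 0.0297²) = 0.054, so the observed effects must differ by about 1.96 × 0.054 = 10.6 points to be flagged, as much as the planned effect itself.

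**The case against.** The strongest answer is that the plan contains no wrong rule. A reader might infer that consistency is to be decided by the p-value in each row, but no passage says so. The plot carries differences and 95% CIs as well, and the analyses are labelled supportive. That stands. What remains is a plan whose stated purpose is consistency and whose visible text gives no measure of it. The supportive label waives Type I error control; it does not supply the missing comparison.

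A reader might also infer that no interaction test is planned at all. The documents do not support that: part of 6.4 is blacked out, and the sample code in SAP Appendix 6 is not visible.

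A third tempting reading is that the 5% floor causes the problem. It admits about 30 patients (20 versus 10), where a test says almost nothing (exact Fisher power 0.6%). But no row that small enters the simulated percentages, and no document shows that any listed level is near 5%. Nor do the documents supply a better cut-off.

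Two objections limit the remedy. Deleting p-values while keeping CIs leaves much of the same impression: at 16% vs 6%, some CI over the 12 factors still includes zero in about 78–79% of successful trials. And SAP 6.3.1 separately plans CMH analyses in patients with prior anti-TNF use, which changes to 6.1.2 and 6.2.2 would leave in place. Both stand.

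**Conclusion.** The point holds as a gap in reporting. The visible SAP text has no treatment-by-subgroup assessment, although consistency is the stated purpose, and the p-values it prints largely track subgroup size. For remission at the planned rates, a uniform effect leaves the prior anti-TNF row non-significant in about half of successful trials and at least one of 24 rows in about 82–88%. No single percentage describes the plan: the result runs from about 28% (response, 12 factors) to 98–99% (remission, region included), and all but the anti-TNF share rests on assumed splits.

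The primary analysis, its error rate and the sample size are unaffected. The mismatch between 6.2.2 and 6.4 on endpoints and the two regions absent from the 6.4 factor follow from the text alone and need no assumption.

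**What to change.** 1. **SAP 6.1.2 and 6.2.2.** Keep the estimate and 95% CI in each row. In place of the within-subgroup p-values, report one heterogeneity p-value per factor on the plotted risk-difference scale: the z-test above for two levels, and its multi-level form (Cochran's Q) for region. A logistic interaction would test odds ratios, which can differ between subgroups even when the risk difference is constant.
2. **Reading.** State that these p-values are descriptive and unadjusted, that consistency is judged from estimates and CIs together with them, and that neither a CI including zero nor a non-significant heterogeneity test settles the question. Refer to this beside the anti-TNF analyses in 6.3.1.
3. **Endpoints.** Make 6.2.2 and 6.4 name the same endpoints.
4. **Region.** Add South America and South Africa to the factor in 6.4, pooled if small.

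If the blacked-out text already contains a heterogeneity test, item 1 reduces to removing the within-subgroup p-values and checking the scale.

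**Cost.** SAP wording and one extra calculation per factor and endpoint; no new data. The downside is chance findings: about 5% of factors, and at least one of 12 in roughly 34–47% of successful trials, will be flagged under a uniform effect. Power to detect real differences is low.

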6.2. Analyses of Key Secondary Efficacy Endpoints

The key secondary efficacy endpoints [a priori ordered] are:

- The proportion of adult patients with a clinical response at Week 10
- The proportion of adult patients with endoscopic improvement at Week 10
- The proportion of adult patients with mucosal healing at Week 10

The ordering of the 3 key secondary endpoints reflects the assigned order of the study objectives as outlined in Section 3 and such testing procedure has been shown to control the FWER at alpha of 0.05 [REDACTED]

6.2.1. Control of Family-wise Type I Error Rate

The primary and 3 key secondary endpoints will be tested in order in a closed, hierarchical testing procedure in order to control the overall Type I error rate for multiple endpoints. If the primary endpoint (Three-component Mayo definition) at Week 10 is statistically significant, the proportion of patients with a clinical response (Three-component Mayo definition) at Week 10 will be tested at the 5% level of significance. If that endpoint is significant, then the proportion of patients with endoscopic improvement at Week 10 will be tested at the 5% level of significance. This testing procedure will continue through each of the 3 key secondary endpoints in the order listed in Section 4.2.2 until an endpoint fails to reach statistical significance, after which all subsequent key secondary endpoints will be considered exploratory. Endpoints listed as other secondary endpoints (Section 4.2.2) will be tested in a nonhierarchical fashion without adjustments for multiplicity.

6.2.2. Primary Analysis of Key Secondary Efficacy Endpoints

The clinical response determined using the 7-day scoring algorithm (Appendix 3.2) and the other two key secondary endpoints (endoscopic improvement and mucosal healing) will be tested using the same type of CMH test as specified for the primary endpoint. For each key secondary endpoint, the same summary and inferential statistics will be reported as specified for the primary analysis of the primary endpoint in Section 6.1.1, including a bar graph showing the percentages by treatment/cohort with the weighted treatment difference, associated two-sided 95% CI and CMH p-value.

Patients without sufficient data to determine clinical response at Week 10 will be analyzed using NRI as described in Appendix 1.3. Patients without central read endoscopy results to determine endoscopic improvement at Week 10 will be analyzed using NRI. Patients without endoscopy or Geboes index results to determine mucosal healing at Week 10 will be analyzed using NRI.

For all key secondary endpoints, patients meeting the TFR prior to the Week 10 efficacy evaluation will be analyzed using NRI as described in Appendix 1.3.

The analysis of each key secondary endpoint will be repeated on each of the subgroups listed in Section 6.4. In addition to reporting the subgroup analyses out in a table, a forest plot showing the weighted treatment differences with associated 95% CI and p-values will be produced.

